## Statistical Analysis Plan

Sample Size. Power for Aim 2 was calculated for 160 adult current daily cigarette smokers using an ANCOVA framework to detect differences between any two study conditions; with n=40 in each of the four conditions in the trial, we will have 80% power to detect medium effect sizes (Cohen's  $f = 0.33$ ) in continuous outcomes (i.e., nicotine beliefs, behavior, subjective ratings), assuming three covariates in the model (i.e., age, gender, cigarettes per day at baseline). In addition, using a two-way analysis of variance framework, 40 participants in each study condition provides 85% power to detect a statistically significant moderation of these same outcomes by the nicotine content of the study cigarettes, assuming that the responses by those in the NCM + NNC condition differ from those in the other three conditions by 1 standard deviation. Sample size for the eye tracking analyses is based on our earlier work that recruited 200 participants to a 2 x 2 factorial design and used the same outcomes (i.e., dwell time, time to first area of interest).

Data Preparation. We will conduct data screening steps similar to Aim 1 including assessing outliers, missing data presence/patterns, and normality/equality of variance assumptions. Non-normal data will be transformed as needed. In all analyses, the assumptions underlying the application of all the statistical methods that are used will be examined, principally using standardized residuals, influence diagnostics, and graphical displays. Where needed, appropriate transformations will be applied to ensure that data meet model assumptions. Descriptive analyses will characterize participants overall and by study condition. Aim 2 eye tracking data will be cleaned and pre-processed using standard procedures from our previous work. Descriptive analyses will characterize participants overall and by study conditions. Bivariate tests will assess for differences in participant characteristics by conditions and examine if any baseline variables that are imbalanced between study groups are associated with primary and secondary outcomes ( $p < .10$ ). Any such variables will be accounted for in analyses as covariates.

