### Analytic Approach.

**Aim 2: Test the impact of NCM (messaging vs. control) and nicotine content of cigarettes (normal vs. reduced) on nicotine beliefs and subsequent use of tobacco and nicotine products using a 2 x 2 factorial design in a sample of 160 adult current smokers followed for 4 weeks.**

*Hypothesis 2a:* Adult smokers in the NCM + normal nicotine content (NNC) cigarette condition will report the fewest false beliefs about nicotine compared to those in the NCM + RNC and control conditions (Control + RNC cigarettes, Control + NNC cigarettes); those in the Control + NNC cigarette condition will report the highest study cigarette use.

*Hypothesis 2b:* Lower subjective ratings of study cigarettes (e.g., strength) will predict greater false beliefs about RNC cigarettes.

Analyses for Aims 1 and 2 employ common measures and a common analytic framework to test the impact of nicotine education on nicotine beliefs and behavior. Primary analyses will use an intention-to-treat approach, employing a general linear mixed model to accommodate missing data. Outcomes for **Aim 2** focus on continuous outcomes (*primary outcome*: nicotine beliefs; *secondary outcomes*: frequency and intensity of nicotine/tobacco use), with the primary hypotheses (**Hypotheses 2a**) focused on the effect of the two interventions (nicotine education and nicotine content of study cigarettes) on these outcomes. Preliminary analyses will examine differences in these outcomes across study conditions at the first post-exposure time point (Week 2) and at the final timepoint (Week 5) using ANCOVA controlling for covariates that are differentially distributed between study groups. These outcomes as well as measures of tobacco use (study cigarette use, topography patterns, CO) will then be analyzed using the general linear model approach to repeated measures analysis. Of primary interest in Aim 2, we will evaluate

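### Covariates enter through a baseline-imbalance screen, so the Week 2 and Week 5 ANCOVAs would seldom adjust for Week 0 nicotine beliefs, and the primary mixed model's use of Week 0 is unstated

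*Combined protocol and SAP*

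**What the plan says.** Three parts of the SAP bear on covariates.

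- **Data Preparation.** "Bivariate tests will assess for differences in participant characteristics by conditions", and the analyst will then "examine if any baseline variables that are imbalanced between study groups are associated with primary and secondary outcomes". A threshold of p < .10 is printed after the association condition. No threshold is given for imbalance. The paragraph ends: "Any such variables will be accounted for in analyses as covariates".
- **Analytic Approach, preliminary analyses.** Outcomes at Week 2 and Week 5 are compared across conditions "using ANCOVA controlling for covariates that are differentially distributed between study groups".
- **Sample Size.** Power is computed "assuming three covariates in the model (i.e., age, gender, cigarettes per day at baseline"). The analysis text does not carry these three forward.

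The primary analysis is by intention to treat, "employing a general linear mixed model to accommodate missing data". Analytic Approach names the interaction of messaging with cigarette type, tested at .05, as the main question. The Study Measures table places nicotine beliefs, the primary outcome, at Weeks 0, 2 and 5, and the Study Protocol section places randomisation at Week 1. No section names Week 0 beliefs as a covariate or says how Week 0 enters the mixed model.

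**The concern.** A baseline variable earns its place in a model by predicting the outcome, not by differing between arms. In a randomised trial any difference at baseline is chance, so a rule that waits for one leaves out the baseline value of the primary outcome in most trials, although it is likely to be the best predictor available. The loss matters more here because the protocol describes 74 participants, while the SAP planned 160.

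The primary model raises a separate problem. Week 0 could be a covariate, a response with its own mean in each arm, or a response with one mean shared by all arms. The effect could be read at Week 5 alone or as change from Week 0. These choices give different standard errors, and the SAP does not choose among them.

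**Working it through.** **Inputs.** From the SAP: 40 per condition, and the effect it uses for moderation, "assuming that the responses by those in the NCM + NNC condition differ from those in the other three conditions by 1 standard deviation". From the protocol: 74 participants. Assumed: a split of 18/18/19/19, complete data, two-sided alpha of .05, and a baseline-outcome correlation (rho) of 0.3, 0.5 or 0.7, since the documents give none.

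**1. The SAP's own figure.** If one cell differs by 1 SD, the interaction contrast is 1 SD. With 40 per cell, SE = √(4 × 1/40) = 0.316 and the noncentrality is 1/0.316 = 3.16 on 156 df. Power is 88.2%, against the stated 85%. With 37 per cell it is 85.6%, so the stated figure is slightly conservative. Nothing below rests on the difference.

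**2. The same test at 74, unadjusted.** SE = √(1/18 + 1/18 + 1/19 + 1/19) = 0.465, and power is 56.4% on 70 df.

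**3. How often Week 0 beliefs are selected.** A four-arm test of a randomised baseline is significant with probability equal to its threshold, and the association condition can only lower that. In 8,000 simulated trials per setting, at rho 0.3/0.5/0.7, selection was 7.5/9.8/10.4% with imbalance tested at .10, and 3.5/4.8/5.4% at .05.

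**4. Power of the ANCOVA interaction test at 74.** Adjusting for Week 0 multiplies the residual variance by 1 − rho², that is 0.91/0.75/0.51.

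| Covariates | rho 0.3 | rho 0.5 | rho 0.7 |
|---|---|---|---|
| Screen at .05 | 57% | 56% | 58% |
| Screen at .10 | 57% | 57% | 59% |
| Week 0 always, plus three covariates given no predictive value | 58% | 66% | 82% |

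Against the .10 screen the gain is about 1–2/9/23 points.

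**5. The same comparison at the planned 160.** Power under the .10 screen is 88.2/89.5/90.5%. Always adjusting for Week 0 alone gives 90.7/95.1/99.3%, a gain of 2.5/5.6/8.8 points.

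**6. Type I error.** Under the screen it is about 4–5% for the interaction.

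**7. Mixed model, Week 5 interaction at 74.** Calculated with compound symmetry over Weeks 0, 2 and 5 and 70 df. The comparator is the model proposed below. With complete data its Week 5 effect is in essence the adjusted ANCOVA, whose unrounded simulated power is 58.6/66.0/82.6%.

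| Form of Week 0 | SE | Power (%) | Loss against proposal (points) |
|---|---|---|---|
| Response, free arm means, Week 5 contrast | 0.465 at every rho | 56.4 at every rho | 2.2/9.6/26.2 |
| Response, free arm means, change from Week 0: SE = 0.465 × √(2(1 − rho)) | 0.550/0.465/0.360 | 43.3/56.4/78.1 | 15.3/9.6/4.5 |
| Response, common mean: SE = 0.465 × √(1 − rho²) | 0.444/0.403/0.332 | 60.4/68.7/84.3 | none |
| Covariate | – | 59.7/68.1/83.8 | none |

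**8. Choosing the form afterwards.** Taking the smallest p-value of the unadjusted, change-score and Week 0-adjusted interaction tests gives a type I error of about 9–11%.

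**The case against.** The strongest reply is that the ANCOVA sentence describes preliminary analyses only. That stands. A reader might infer that the primary analysis also seldom adjusts for baseline beliefs, and the documents do not show this. A repeated-measures model that takes Week 0 as a response with a common mean already uses it fully. The Missing data paragraph does say that earlier periods inform later ones, but it is explaining incomplete records and does not settle the role of Week 0. For the primary model the fault is therefore under-specification.

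It can also be said that Data Preparation states which variables will be included and does not forbid others, and that the third moderation step adds cigarette condition outside the screen. This is fair, but cigarette condition is a randomised factor, the ANCOVA sentence describes its covariates as the imbalanced ones, and no section supplies Week 0 beliefs by another route.

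The correlation is assumed, and at 0.3 the ANCOVA gain is only 1–2 points. That also stands.

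Some readings would make the problem look larger or less certain:

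- Week 0 beliefs are never screened because they are not participant characteristics. The same sentence goes on to cover any baseline variable.
- The two factors are screened separately, which raises selection to about 1 in 5. The protocol randomises to four groups and the SAP sizes four conditions, so a four-arm test fits better.
- Each belief scale is screened on its own, so some are adjusted and others not. No section says so, and the four scales are listed only in the exploratory eye-tracking text.

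**Conclusion.** The point holds in two parts. First, the screen makes adjustment for the primary outcome's baseline a rare, chance event in the preliminary ANCOVAs, and it is also the general route by which covariates join other models. At 74 participants the cost is small if rho is 0.3 and substantial from 0.5 upward. At the planned 160 it is smaller. Second, the primary mixed model lacks a stated form for Week 0 and a stated time contrast for the interaction. The loss there is nil if Week 0 is already a covariate or has a common mean. It reaches about 26 points only if the least favourable form is paired with a correlation of 0.7. A figure of 28 points comes from comparing with a model that omits age, gender and cigarettes per day, which is not the model proposed.

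A reader might infer that the screen invalidates the tests. It does not: its type I error stays near the nominal level. Nor is the matter purely one of precision, because an open model form can be settled after the data are seen. The 9–11% error rate describes that worst case. Nothing in the documents shows that it has happened.

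All power figures assume complete data, near-equal allocation and the SAP's own 1-SD effect.

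**What to change.** - Drop the imbalance screen as the rule for admitting covariates.
- In the Week 2 and Week 5 ANCOVAs and in the mixed model, adjust for the Week 0 value of the same outcome, either as a covariate or as a response with a common Week 0 mean. Add the three covariates that the power section already assumes: age, gender and baseline cigarettes per day.
- State the mixed-model form and the time contrast on which the interaction will be tested.
- For an outcome with no Week 0 value, use the three covariates alone. The Study Measures table and the Hypothesis 2b analysis disagree on whether subjective ratings have a Week 0 value. That is a separate matter to reconcile.

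The cost is SAP wording, variables already collected, and at most four residual degrees of freedom (70 − 4 = 66 at 74 participants). If the three extra covariates predict nothing, including them loses about 2 points of power.

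The protocol is written in the past tense and does not show whether outcomes have been examined. If they have, label the adjusted model post hoc and report it beside the analysis as originally planned.

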## Study Protocol

The current study tested the impact of multiple exposures to a brief nicotine corrective messaging intervention and nicotine content of study cigarettes on nicotine beliefs and subsequent use of tobacco and nicotine products in a 28-day lab-based study of 74 adults who smoke cigarettes daily. Data were collected at the University of Pennsylvania Center for Interdisciplinary Research on Nicotine Addiction. A parallel population-based study of exposure to nicotine corrective messaging was conducted in adult smokers and non-smokers followed for 12 weeks (NCT04805515).

The lab-based study was a prospective, randomized factorial trial of nicotine corrective messaging (NCM vs. control) and nicotine content of cigarettes (normal vs. reduced) in current daily adult cigarette smokers (minimum 5 daily cigarettes for the past year, carbon monoxide (CO) at least 5 parts per million at Week 0, and no current use of other tobacco or nicotine containing products) for a 35-day protocol. Recruitment occurred through community and campus bulletin boards, local newspapers, radio and television ads, and previous participants who agreed to be re-contacted for non-cessation or non-treatment studies. At the baseline visit (Week 0), eligible, consenting participants provided a CO sample, complete demographic and smoking history measures, and measures of nicotine beliefs and intentions/use of nicotine and tobacco products (see Study Measures). They also provided breath and urine samples for biomarker assessment and continued to smoke their usual brand cigarettes to assess their baseline cigarette smoking behavior. Participants were instructed to continue smoking their own brand cigarettes and collect used filters as a verified count of daily smoking using re-sealable bags provided, while also recording their smoking in a calendar. Participants returned on Day 7 (Week 1; end of baseline), returned used cigarette filters, and were randomized to one of four groups: 1) Nicotine Corrective Messaging (NCM) + RNC cigarettes, 2) NCM + normal nicotine content (NNC) cigarettes, 3) Control + RNC cigarettes, or 4) Control + NNC cigarettes. Participants receiving normal nicotine content or reduced nicotine content cigarettes were explicitly told which product they have been given (i.e., unblinded).

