The Nicotine Corrective Messaging (NCM) intervention condition was based on messages tested in our team's pilot study. It included six original messages and two new messages addressing nicotine in cigarette and e-cigarette products that were adapted from several evidence-based sources to be more accessible to a lay audience. The sources consisted of FDA's 2017 comprehensive plan for tobacco and nicotine regulation, FDA's 2013 modifications to labeling of NRT products for over-the-counter human use, the 2014 U.S. Surgeon General's Report on the Health Consequences of Smoking, reports on carcinogens from the International Agency for Research on Cancer, and the NASEM report on the "Public Health Consequences of E-cigarettes." Participants in the NCM condition were exposed to all eight messages in the same order at each exposure.

Participants in the NCM condition received their first exposure to the study messages on Day 7 in the lab. Eye tracking was assessed during a five-second exposure to each educational message, equating to a minimum 40-second exposure. At the end of the session, all participants left with study-provided cigarettes to last until the next visit. Participants continued to collect used filters and record daily number of study cigarettes, non-study cigarettes, and other nicotine or tobacco products used each day for the duration of the study. At lab visits on Days 14 (Week 2), 21 (Week 3), and 28 (Week 4), daily nicotine/tobacco use calendars and used filters were collected at the start of the visit. At the Week 2 visit, all participants completed the first post-exposure measures of nicotine beliefs and intentions/use of nicotine and tobacco products. In visits at Weeks 2-4, participants smoked their study product with CO collected at the start and each smoking session videotaped to extract smoking

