whether using study cigarettes with a known nicotine content (i.e., normal or reduced) moderates the effect of NCM on our primary and secondary outcomes by incorporating an interaction between NCM condition (NCM/control) and study cigarette condition (NNC/RNC) through the following steps: 1) bivariate analyses, to determine if outcomes vary by these variables; 2) testing whether study cigarette condition moderates ( $p < .05$ ) experimental effects in the models above; if so, performing post-hoc statistical testing to examine the direction and magnitude of the moderation; 3) if no evidence of moderation exists, including study cigarette condition as a covariate.

Our previous work highlights that assessing perceptions of RNC cigarettes that find an association between participants perceiving that their assigned product is low nicotine and reporting lower harm perceptions of the product. To address **Hypothesis 2b**, we will also use autoregressive, cross-lagged panel analysis to examine the direction of the relationships between subjective ratings and nicotine beliefs over three timepoints (Weeks 0, 2, and 5) and whether the regression paths vary in magnitude by study condition.

As in Aim 1, our exploratory analyses will focus on three areas: 1) potential moderators of the relationship between intervention condition and the study outcomes; 2) nicotine beliefs as a potential mediator of the relationship between intervention condition and constructs identified in the Theory of Planned Behavior (i.e., nicotine-related attitudes, norms, behavioral control, and nicotine/tobacco intentions and use); and 3) the relationship between visual attention to nicotine education messages and nicotine beliefs in the participants exposed to the NCM intervention.

For the first area (*moderation*), we will conduct exploratory analyses using the same steps described for Hypothesis 2a to determine whether there are potential moderators of the relationship between the study condition (NCM + RNC, NCM + NNC, Control + RNC, Control + NNC) and outcomes, specifically age, gender, baseline cancer beliefs and cancer risk behaviors.

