For the second area (*mediation*), we will draw from traditional mediation frameworks and use robust methods to explore the relationships outlined in our theoretical framework and whether changes in nicotine beliefs post-exposure (Weeks 2, 3, 4) influence nicotine-related attitudes, norms, behavioral control, intention, and behavior at the final assessment (Week 5). To complement Aim 1 analyses, we will examine whether nicotine beliefs at Week 2 are associated with these Week 5 outcomes using bivariate statistics and the general linear model-based analysis accounting for any covariates as described above. Where these preliminary steps indicate potential correlation between nicotine beliefs and study outcomes ( $p < .05$ ), we will test for mediation by estimating the indirect effects of nicotine beliefs on follow-up outcomes via the study condition using a bias-corrected bootstrapping method with 1,000 resamples. This approach estimates indirect (i.e., mediation) effects and produces bias-corrected asymmetric 95% CIs correcting for non-normality of the distribution of indirect effects and providing higher power and better control over the Type I error rate versus traditional approaches to test mediation. Asymmetric 95% confidence intervals around indirect effect estimates for nicotine beliefs that do not include zero will be interpreted to indicate significant mediation.

For the third area (*visual attention*), we will identify the regions of interest (ROIs) in each nicotine education message based on responses to the Aim 1/Wave 1 heatmap task. Using eye-tracking, we will explore whether attention to the ROIs (i.e., dwell time, fixations) is correlated with scores on the nicotine beliefs scales (i.e., nicotine, NRT, e-cigarette, RNC cigarette beliefs) at the same assessment (Weeks 1-4). Given the content of messages in the nicotine education condition, we will be able to assess whether attention to specific ROIs is correlated with specific beliefs (i.e., whether attention to a specific ROI within the “Nicotine does not cause cancer” is correlated with response to the nicotine belief item regarding nicotine causing cancer). We will also be able to explore the prospective relationship between visual attention to the nicotine

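### The exploratory mediation test is worded with exposure and mediator swapped; run as written, it would almost always miss complete mediation by nicotine beliefs

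*Combined protocol and SAP*

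**What the plan says.** The list of exploratory areas in the SAP's Analytic Approach gives the second area as "nicotine beliefs as a potential mediator of the relationship between intervention condition and constructs identified in the Theory of Planned Behavior". Condition is the exposure, beliefs are the mediator, and attitudes, norms, behavioral control, intentions and use are the outcomes. The mediation paragraph opens in the same direction, with post-exposure beliefs influencing Week 5 outcomes.

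The procedure then has three parts:

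- **Screen.** The association of Week 2 beliefs with Week 5 outcomes is examined by bivariate statistics and a general linear model with covariates. The test follows at p < .05: "Where these preliminary steps indicate potential correlation between nicotine beliefs and study outcomes".
- **Test.** Mediation is tested by "estimating the indirect effects of nicotine beliefs on follow-up outcomes via the study condition", "using a bias-corrected bootstrapping method with 1,000 resamples".
- **Decision rule.** "Asymmetric 95% confidence intervals around indirect effect estimates for nicotine beliefs that do not include zero will be interpreted to indicate significant mediation".

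On timing, the Study Protocol section says that participants returned on Day 7 and "were randomized to one of four groups". It adds: "At the Week 2 visit, all participants completed the first post-exposure measures of nicotine beliefs".

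**The concern.** An indirect effect of one variable on another via a third makes the first the exposure and the third the mediator. Read that way, the test sentence puts beliefs in the place of the exposure and the randomised condition in the place of the mediator, the reverse of the aim stated just before it. Week 2 beliefs cannot cause an assignment made at Week 1. Nor can Week 0 beliefs, because assignment is random.

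This is the only sentence that says which indirect effect is bootstrapped, and the decision rule attaches a firm conclusion to its interval. If the code follows it, the reported estimate and interval do not measure whether beliefs carry the intervention's effect to attitudes, intentions and use.

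**Working it through.** **Inputs from the documents.** Roles, timing, screen, bootstrap and decision rule are as set out above. N is 74 (Study Protocol) or 160 (SAP, Sample Size). The plan gives no power figure or path value for mediation, so there is no stated figure to reproduce.

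**Assumed inputs.** All path values are assumptions. The value 0.66 is taken from the sample-size effect f = 0.33 (two equal groups: d = 2 × 0.33 = 0.66). The value 1 is a larger alternative of 1 SD. The belief-to-outcome slope is 0 or 0.5. Condition is one binary factor split equally, and residual SDs are 1.

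**Algebra.** Let X be condition, M Week 2 beliefs and Y the Week 5 outcome:

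- M = aX + error
- Y = bM + c′X + error

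The intended indirect effect is a × b. With the roles as written, the first factor is the slope of X on M, a* = 0.25a / (0.25a² + 1), where 0.25 is the variance of X. The second is the coefficient of X on Y given M, which is c′, the direct effect. The tested product is therefore a* × c′, and b does not appear in it.

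For a = 0.66, a* = 0.165 / 1.1089 = 0.149. Then:

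- Complete mediation (b = 0.5, c′ = 0): intended 0.66 × 0.5 = 0.33; as written 0.149 × 0 = 0.
- Partial mediation (b = 0.5, c′ = 0.66): intended 0.33; as written 0.149 × 0.66 = 0.098.
- Direct effect only (b = 0, c′ = 0.66): intended 0; as written 0.098 again.

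The written product is the same whether beliefs carry part of the effect or none of it. For a = c′ = 1 and b = 0, a* = 0.25 / 1.25 = 0.2 and the product is 0.2. Simulated means of the written product at N=160 agree: 0.000, 0.101, 0.100 and 0.205.

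**Simulation.** The table rests on 600 trials per scenario, with the bias-corrected bootstrap and 1,000 resamples. The Monte Carlo standard error is at most √(0.25/600), about 2 points. Entries are the percentage of trials declaring mediation. The first two result columns apply the bivariate p < .05 screen; the last also requires the belief-outcome association to hold adjusted for condition.

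| Scenario (a, b, c′) | N | Correct roles | As written | As written, adjusted screen too |
|---|---|---|---|---|
| Complete (0.66, 0.5, 0) | 74 | 81 | 8 | 8 |
| | 160 | 99.5 | 5 | 5 |
| Partial (0.66, 0.5, 0.66) | 74 | 85 | 70 | 69 |
| | 160 | 99 | 97 | 97 |
| Direct only (0.66, 0, 0.66) | 74 | 5 | 11 | 3 |
| | 160 | 4 | 22 | 2 |
| Direct only (1, 0, 1) | 74 | 5 | 41 | 3 |
| | 160 | 3 | 76 | 3 |
| Direct only, no belief shift (0, 0, 0.66) | 74 | 1 | 1 | 0.5 |
| | 160 | 0.5 | 0.7 | 0.2 |

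With this table, repeat runs give these ranges:

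- **Complete mediation:** 81-84% with correct roles against 6-8% as written at N=74; 99-100% against 5-9% at N=160.
- **Partial mediation, as written:** 64-70% at N=74 and 96-97% at N=160.
- **Direct effect only, as written, bivariate screen:** 8-26% at 0.66 and 38-76% at 1 SD.

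**The case against.** The strongest reply is that this is a drafting slip. The list of exploratory areas gives the right roles, the mediation paragraph opens in the right direction and appeals to traditional mediation frameworks, and the decision rule is compatible with beliefs as the mediator. Every consequence above assumes that someone codes the odd sentence literally. That is fair: nothing in the documents shows that the reversed model was intended or run. It does not remove the point, because this sentence defines the quantity to be bootstrapped.

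Three stronger readings are tempting, and the documents do not support them.

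- **A reader might infer that any true mediation would be reported as none, or that conclusions would come out roughly opposite.** Only complete mediation is lost. Under the assumed partial mediation the written model usually still signals, because a direct effect is present.
- **A reader might infer that a pure direct effect would generally be called mediation.** Condition must also shift beliefs, and the screen must be passed. With no belief shift the rate is about 1%. Whether the screen adjusts for condition is not stated, since the linear-model step refers only to covariates described earlier. If it does, false mediation falls to about 2-3%.
- **A reader might infer that the screen is reversed as well.** It is not. Beliefs to outcome is the second path of the correct model, and condition to beliefs is the primary analysis under Hypothesis 2a.

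The simulation also reduces the design to one binary factor. The moderation paragraph defines study condition as four groups, which as a literal mediator would have no single product term. The percentages illustrate the mechanism and do not predict this trial.

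**Conclusion.** The point holds: the test sentence swaps exposure and mediator, contradicts the plan's own aim and describes a path that randomisation rules out. It is a wrong analysis rule as written, not a missing detail.

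The loss under complete mediation follows from algebra and does not depend on the chosen paths: the tested product is zero whenever the direct effect is zero. The exact rates, the partial-mediation result and the false-mediation rates do depend on assumed paths, on a single binary factor and, for the last, on an unstated feature of the screen. Where the written model does signal, its estimate and interval still describe the wrong quantity (0.098 against 0.33 in the partial case).

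Severity is low to moderate. The analysis is exploratory and no primary or secondary hypothesis test rests on it.

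**What to change.** Replace the test sentence in the mediation paragraph with wording such as:

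> We will estimate the indirect effect of study condition on each Week 5 outcome via Week 2 nicotine beliefs, where a is the effect of condition on Week 2 beliefs, b is the effect of Week 2 beliefs on the Week 5 outcome given condition, and the bias-corrected bootstrap interval is for a × b.

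Enter condition as the randomised factors already used in the plan's other models, and say to which contrast each a × b refers. Narrowing condition to messaging against control is not needed to correct the swap. Week 2 is the mediator time point because the Study Measures table has beliefs at Weeks 0, 2 and 5 only.

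State whether the linear-model screen includes condition. Because the Study Protocol section describes the trial in the past tense, confirm that the code run, or to be run, follows the corrected direction.

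The cost is one sentence of SAP text and a check of the matching code. No new data are needed.

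### Exploratory mediation is declared from a 1,000-resample bootstrap interval with no fixed seed, so a borderline result can change with the seed (about 0.3% to 5% per test)

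*Combined protocol and SAP*

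**What the plan says.** The mediation analysis is the second of three areas that the SAP (Analytic Approach) introduces with "As in Aim 1, our exploratory analyses will focus on three areas". It asks whether nicotine beliefs after exposure carry the effect of study condition to five Week 5 constructs: norms, attitudes, behavioral control, intention and behavior.

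The procedure has two steps. First, the association of Week 2 beliefs with each Week 5 construct is examined. Only where these steps "indicate potential correlation between nicotine beliefs and study outcomes" at p < .05 does the plan go on to mediation. Second, the indirect effect is estimated "using a bias-corrected bootstrapping method with 1,000 resamples", a method that in the SAP's words "produces bias-corrected asymmetric 95% CIs". The decision rule is binary: "Asymmetric 95% confidence intervals around indirect effect estimates for nicotine beliefs that do not include zero will be interpreted to indicate significant mediation".

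The documents give no random seed, no check of Monte Carlo error, no assumed size for either path, and no power for this test.

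**The concern.** A bootstrap interval is itself a simulation estimate. With 1,000 resamples, a 2.5% tail holds about 0.025 × 1,000 = 25 draws. The bias-correction constant is estimated from the same draws and enters the limits doubled, which adds further noise. When the observed indirect effect puts a limit close to zero, this noise can decide which side of zero the limit falls on.

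The rule turns that into a yes/no statement about significance. Two analysts with the same data, model and SAP could then report opposite conclusions, and the SAP would not say which is the planned one. Percentile intervals with 1,000 resamples share most of the problem, so this is largely separate from the choice of interval type.

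**Working it through.** **Inputs.** From the SAP, Analytic Approach: B = 1,000 resamples, bias-corrected 95% interval, mediation declared if zero is excluded, prior screen at p < .05. Sample size: the SAP states "Power for Aim 2 was calculated for 160 adult current daily cigarette smokers", while the Study Protocol describes the work as carried out "in a 28-day lab-based study of 74 adults who smoke cigarettes daily"; both sizes were used. The paths a (condition to beliefs) and b (beliefs to outcome) are assumptions, because the documents give none. The plan states no figure for seed-to-seed change, so there is nothing to reproduce first.

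**Step 1: Monte Carlo error of the decision, on the z scale.** With p = 0.025, φ(1.96) = 0.0584 and φ(0) = 0.3989:

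- Percentile interval: √[p(1−p)/B] / φ(1.96) = √(0.025 × 0.975 / 1,000) / 0.0584 = 0.0845, variance 0.00714.
- Noise from the doubled bias constant: 4 × 0.25 / (B × φ(0)²) = 0.00628.
- Covariance term: 4 × p × 0.5 / (B × φ(1.96) × φ(0)) = 0.00214.
- Bias-corrected interval: s = √(0.00714 + 0.00628 − 0.00214) = 0.106.

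**Step 2: chance that two seeds disagree.** Let q be the probability, given the data, that one run excludes zero. The rate is E[2q(1−q)]. For a statistic z ~ N(θ, 1) this is close to (2s/√π) × [φ(1.96 − θ) + φ(1.96 + θ)], with 2s/√π = 0.120:

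- θ = 0: 0.120 × (0.058 + 0.058) = 1.4%
- θ = 1: 0.120 × (0.252 + 0.005) = 3.1%
- θ = 1.96 (about 50% power): 0.120 × 0.399 = 4.8%
- θ = 2.8 (about 80% power): 0.120 × 0.280 = 3.4%

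**Step 3: simulation of the indirect effect itself.** X is NCM or control, M = aX + e, Y = bM + e. There were 2,000 datasets per scenario, each with 10 independent sets of 1,000 resamples and bias-corrected intervals. The simulation standard error is about 0.1 to 0.3 points.

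| a | b | N=74: excludes zero | N=74: two seeds disagree | N=160: excludes zero | N=160: two seeds disagree |
|---|---|---|---|---|---|
| 0 | 0 | 0.6% | 0.4% | 0.6% | 0.3% |
| 0 | 0.39 | 8.2% | 2.2% | 7.6% | 1.5% |
| 0.3 | 0.3 | 23.3% | 4.2% | 54.4% | 4.8% |
| 0.39 | 0.39 | 45.1% | 4.9% | 73.0% | 3.1% |
| 0.5 | 0.3 | 48.8% | 4.5% | 88.6% | 2.3% |
| 0.66 | 0.39 | 77.3% | 3.8% | 99.0% | 0.4% |

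With both paths null, the simulated rate is below the 1.4% of step 2 because the product of two null paths is rarely significant at all (0.6%). Other runs of the N = 74, a = 0.5, b = 0.3 case gave 5.2% and 5.3–5.7%. A small run of 400 datasets gave 6.9% with a standard error of 0.8. The 2,000-dataset value and the analytic maximum of 4.8% are the firmer guide.

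**Step 4: effect of the p < .05 screen.** Among datasets that pass it, the rates with at least one non-null path are similar (0.4% to 5.0%). With both paths null the rate among those that pass is about 3%, but this rests on 99 and 110 datasets (standard error about 1 point). The screen therefore reduces the number of tests but does not stabilise those that remain.

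**Step 5: more resamples.** s scales with 1/√B. The worst case (about 50% power) is 4.8% at 1,000, 3.4% at 2,000, 2.1% at 5,000, 1.5% at 10,000 and 1.1% at 20,000. A simulation with 10,000 resamples (N = 74, a = 0.5, b = 0.3) gave about 1.3%.

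**The case against.** The case for leaving this alone is fair in several respects. The analysis is exploratory, and no primary or secondary conclusion rests on it. Conclusions flip only where a limit already lies near zero, which a careful reader would call borderline under any seed. Monte Carlo noise of 0.106 against a sampling SD of 1 raises the total SD by √(1 + 0.106²) − 1 = 0.6%, so Type I error and power hardly move. Against the answer from unlimited resamples, one run of 1,000 is wrong at most about 3.4% of the time. The simulation uses one binary condition and no covariates, whereas the SAP has four conditions and adjusts for covariates, so the percentages are indicative. All of this stands, and it keeps the point minor.

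It could also be said that resample count and seed are programming details. That carries less weight here, because the SAP does fix the count and attaches the word significant to the outcome.

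Two stronger readings are tempting, and the documents support neither:

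- A reader might infer that 1 in 20 mediation conclusions depends on the seed. That is roughly the maximum, reached near 50% power. Without an assumed indirect effect, the documents place the trial nowhere in particular on the range.
- A reader might multiply up over the five Week 5 constructs: 1 − 0.95⁵ = 22.6%. This needs all five to pass the p < .05 screen, all to sit at the worst-case rate, and all to be independent. The outcomes come from the same participants and share the same condition and mediator, and the number that will pass the screen is unknown.

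**Conclusion.** The concern holds as a minor reproducibility point. Under the SAP as written, two seeds can give opposite mediation conclusions on the same data with probability of about 0.3% to 5% per test. Where a given test falls depends on path sizes that the documents do not state: near 5% at about 50% power, 3% to 4% near 75% to 80% power, about 1.5% to 2% when only the b path is non-zero, and below 1% over all datasets when both paths are null or power is near 99%. These figures assume a two-group comparison without covariates and approximately normal errors. They say nothing against the validity of the bootstrap in general, and they do not touch the primary or secondary analyses.

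**What to change.** In the SAP's mediation paragraph, replace the stated resample count with at least 10,000 and add a random-number seed fixed before the analysis is run. Both parts are needed: a seed alone makes the result repeatable but leaves it as arbitrary as before, and more resamples alone still leave about 1.5% disagreement in the worst case. The change applies equally if a percentile interval is used.

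The Study Protocol is written in the past tense. If the analysis has already been run, rerun it with the larger count, report the seed, and say so where any conclusion differs.

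The cost is one number and one short clause in the SAP, plus seconds to minutes of computing. Nothing in the design, the data collection or the other analyses changes.
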